10.1.4.5 Lost to Follow-up

A subject will be considered lost to follow-up if he/she does not appear for the scheduled study visit for two (2) consecutive visits or does not return for a final visit, and study personnel is unable to contact the subject.

Some actively enrolled subjects will not return for follow-up exams on time. Study personnel must make a reasonable effort to contact the subject and document the following contact attempts before declaring a subject to be lost to follow-up: the subject has been contacted according to the site's policies, but no fewer than two documented phone contacts and one certified letter without response. Copies of all attempts to reach the subjects by mail or email and/or the attempts to contact the subject via other means should be documented, and that documentation should be kept with the subject's source documents.

Confidential and Proprietary

This document contains confidential and proprietary information on Smith & Nephew PLC and Smith & Nephew, Inc. and is only available to Smith & Nephew and its manufacturers. Without prior written approval of Smith & Nephew, the content cannot be replicated, printed totally/partially or disclosed in any other way, and anyone must use it as per the requirements, either expressed or implied by Smith & Nephew.

Study Protocol - Device	Smith+Nephew
A Prospective, Multi-center, Randomized Clinical Study to Evaluate the Safety and Effectiveness of Biosure Regenesorb Interference Screw in Arthroscopic Reconstruction of Cruciate Ligaments in Chinese Patients	Study No.: BIOSURE RG.SMD.PMA.2019.01
	Version: V2.0/July 3rd, 2020
	Page 30 of 74

10.1.4.6 Time of enrollment

The study enrollment can be started only after the Ethics Committee has approved and signed a clinical trial agreement at each site. Before the enrollment, the relevant procedures and requirements should be completed according to the regulations of relevant departments. The competitive enrollment is taken in the study with a preliminarily estimated time of 12 months. The enrollment time can be adjusted according to the actual situation.

Subjects who have completed the informed consent form and have been assigned a random number are considered to be enrolled.

10.1.4.7 Duration of the trial

The enrollment of subjects is planned to last for about 12 months. The primary endpoint of study is Lysholm score at 12 months after operation. Considering the need of bone tissue ingrowth and patient functional recovery, the follow-up of this study should last throughout 12 months after operation. In this trial, a summary of 12-month follow-up data will be reported to NMPA, and 24-month follow-up data will be observed. The specific duration will be adjusted according to the actual situation.

10.1.4.8 Expected duration of participation of each subject

The duration of participation of each subject in the clinical trial is about 12 months with long-term observation for 24 months, the data of which may be adjusted according to the visit window specified in the protocol due to the specific circumstances.

10.1.4.9 Number of subjects

Number of subjects required for the entire clinical trial is about 140. 70 subjects each in the investigational group and control group. For the number of subjects, see the chapter of sample size calculation.

10.1.5 Efficacy evaluation method

10.1.5.1 Primary efficacy endpoints

Confidential and Proprietary

This document contains confidential and proprietary information on Smith & Nephew PLC and Smith & Nephew, Inc. and is only available to Smith & Nephew and its manufacturers. Without prior written approval of Smith & Nephew, the content cannot be replicated, printed totally/partially or disclosed in any other way, and anyone must use it as per the requirements, either expressed or implied by Smith & Nephew.

Study Protocol - Device	Smith+Nephew
A Prospective, Multi-center, Randomized Clinical Study to Evaluate the Safety and Effectiveness of Biosure Regenesorb Interference Screw in Arthroscopic Reconstruction of Cruciate Ligaments in Chinese Patients	Study No.: BIOSURE RG.SMD.PMA.2019.01
	Version: V2.0/July 3rd, 2020
	Page 31 of 74

The primary study endpoint is the Lysholm score at Month 12 after operation.

The Lysholm score, a knee scoring system created by Lysholm and Gillqui in 1982 and revised in 1985, has been applied in many international literature articles, and its reliability, effectiveness and sensitivity have been demonstrated in international literature. The Lysholm score is a scoring scale the most commonly used before and after arthroscopic knee surgery. A preliminary assessment can be made for the level of motion of patients with different intensity. The scale evaluates functions of patients based on 8 items: limp, support, interlocking, pain, instability, swelling, stair climbing and squatting. The total Lysholm score is 0-100. Pain and instability account for a higher proportion in this score. The knee functions of patients are considered excellent when the score is 95-100, good when 84-94, fair when 65-83 and poor when less than 65. The measurement takes about 3-5 min. The Lysholm score emphasizes the patient's subjective perception of symptoms and grade dysfunction in combination with the score and the level of daily activity. Studies have shown that the scale is the most reliable for patients undergoing cruciate ligament reconstruction and the difference in score is more significant when it is used to evaluate patients who self-limit activities.

10.1.5.2 Secondary efficacy endpoints

- Lysholm Score (Month 6, Month 24)
- International Knee Documentation Committee (IKDC) score (at months 6, 12 and 24)

The scoring scale was proposed in 2000 after being repeatedly revised by major sports medicine and medical organizations in Europe and America. The scale is composed of a knee evaluation form (10 items) and a knee ligament examination form (8 items), involving joint pain, sport level and ability of daily activities. The total score is 0-100. The IKDC scale is for evaluating the symptoms, functions and physical activities of the knee joint, helping compare different knee diseases.

- Drawer Test (Month 6, Month 12, Month 24)

Anterior drawer test: It is used for ACL examination. The patient should be supine with the knees flexed to 90 degrees and the feet flat on table and keep relaxed. The examiner sits on the examination table against the patient feet for fixation, grasps the tibia of the knee and draws the shank forward. The patient will be diagnosed with forward straight instability if the tibia is forward displaced 5 mm more than the uninjured side.

Posterior drawer test: It is used for PCL examination. The patient should be supine with the knees flexed to 90 degrees. The examiner places both hands behind the knee joint, with the thumbs on the extensor aspect. The proximal end of shank is repeatedly drawn backward. The posterior displacement of the tibia along the femur suggests partial or complete CL rupture.

Confidential and Proprietary

This document contains confidential and proprietary information on Smith & Nephew PLC and Smith & Nephew, Inc. and is only available to Smith & Nephew and its manufacturers. Without prior written approval of Smith & Nephew, the content cannot be replicated, printed totally/partially or disclosed in any other way, and anyone must use it as per the requirements, either expressed or implied by Smith & Nephew.

Study Protocol - Device	Smith+Nephew
A Prospective, Multi-center, Randomized Clinical Study to Evaluate the Safety and Effectiveness of Biosure Regenesorb Interference Screw in Arthroscopic Reconstruction of Cruciate Ligaments in Chinese Patients	Study No.: BIOSURE RG.SMD.PMA.2019.01
	Version: V2.0/July 3rd, 2020
	Page 32 of 74

- Lachman Test (Month 6, Month 12, Month 24)

The Lachman test is carried out at injured and uninjured sides simultaneously. The patient should be supine with the knees flexed to 20-30 degrees and the injured limb slightly rotated outward. The examiner stands beside the injured side, immobilizes the lower end of the femur with one hand, and presses the posterior side of the upper end of the tibia forward (Lachman test) or backward (reverse Lachman test). A positive test result is got. Positive results suggest ACL or PCL injury.

- Imaging evaluation (Month 6, Month 12, Month 24)

Take X-ray films, CT images and MRI images of the knee before operation, intraoperative - post-operative (Day 0-5) (only X-ray films and CT images), 6, 12, 24 months after operation, respectively. Observe bone ingrowth and bone absorption, etc. All imaging observations are to be reported on the CRF.

Other imaging films taken are at the discretion of the individual Investigator.

Although imaging evaluation will be performed at each site by the investigator, all imaging examination data will be stored in electronic DICOM format at the site until they are no longer needed in case further evaluation by an independent centralized reviewer is requested by NMPA. All imaging examination data must be modified in order to protect subjects' identity if they are sent to Smith & Nephew, or designee, for independent review. If independent review is required, it will be done by a board certified radiologist selected by the Sponsor based on experience in orthopaedics and joint replacement imaging.

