10.1.2 Study method selection and justification

This is a prospective, randomized, multi-center clinical study designed to compare the safety and effectiveness of Biosure Regenesorb Interference Screw versus the BIOSURE HA Interference Screw in arthroscopic cruciate ligament reconstruction in Chinese subjects.

This clinical trial is a clinical trial for registration of medical device, so it is required to follow the requirements of relevant regulations issued by National Medical Products Administration (NMPA). This study is designed as a prospective, multi-center, randomized, evaluator-blinded, parallel-controlled study.

The subjects meeting the inclusion/exclusion criteria specified in the protocol will be randomized to receive implantation with the investigational product or control product. A total of 140 subjects are planned to be included in about 4 study sites. The average number of subjects should be included in each study site as mean as possible. The number of subjects included in each study site should be no more than 70 cases. The clinical follow-up evaluation will be conducted at 6, 12 and 24 months respectively after operation. The telephone follow-up should also be conducted at 6 weeks, 3, 4.5 and 9 months respectively after operation. In this study, 12-month follow-up data will be submitted for registration and 24-month follow-up will be made to observe the long-term performance and absorbability of the investigational device.

Confidential and Proprietary

This document contains confidential and proprietary information on Smith & Nephew PLC and Smith & Nephew, Inc. and is only available to Smith & Nephew and its manufacturers. Without prior written approval of Smith & Nephew, the content cannot be replicated, printed totally/partially or disclosed in any other way, and anyone must use it as per the requirements, either expressed or implied by Smith & Nephew.

Study Protocol - Device	Smith+Nephew
A Prospective, Multi-center, Randomized Clinical Study to Evaluate the Safety and Effectiveness of Biosure Regenesorb Interference Screw in Arthroscopic Reconstruction of Cruciate Ligaments in Chinese Patients	Study No.: BIOSURE RG.SMD.PMA.2019.01
	Version: V2.0/July 3rd, 2020
	Page 25 of 74

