10.1.3.2 Blinding

To avoid the bias occurring to the research design, we appoint an independent rator in each study site, who is blinded and responsible for completing scoring at each follow-up.

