10.1.3.5 Consistency of score

The training on the consistency of the scale should be provided to the scorer of primary endpoint and secondary endpoint evaluation (such as Lysholm score, IKDC score, drawer test and lachman score) in each site, ensuring that the scorer have consistent understanding and use of the scale, thus reducing the bias between scorers.

Confidential and Proprietary

This document contains confidential and proprietary information on Smith & Nephew PLC and Smith & Nephew, Inc. and is only available to Smith & Nephew and its manufacturers. Without prior written approval of Smith & Nephew, the content cannot be replicated, printed totally/partially or disclosed in any other way, and anyone must use it as per the requirements, either expressed or implied by Smith & Nephew.

Study Protocol - Device	Smith+Nephew
A Prospective, Multi-center, Randomized Clinical Study to Evaluate the Safety and Effectiveness of Biosure Regenesorb Interference Screw in Arthroscopic Reconstruction of Cruciate Ligaments in Chinese Patients	Study No.: BIOSURE RG.SMD.PMA.2019.01
	Version: V2.0/July 3rd, 2020
	Page 26 of 74

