10.1.3.6 Imaging evaluation

The imaging observation indicators are reasonable and necessary indicators for the evaluation of arthroscopic repair of soft tissues, but not included in the Lysholm score. In order to reflect the importance of imaging, imaging evaluation will be performed pre-op, 6, 12 and 24 months post-op.

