10.2.2.9 Imaging examination

Take X-ray films, CT images and MRI images of the knee joint pre-operation, intraoperative-postoperative (Day 0-5) (X-ray film and CT image), 6- and 12- month follow-up after operation, respectively. All imaging observations are to be reported on the CRF. Postoperative device-related and surgical adverse events are to be reported.

Confidential and Proprietary

This document contains confidential and proprietary information on Smith & Nephew PLC and Smith & Nephew, Inc. and is only available to Smith & Nephew and its manufacturers. Without prior written approval of Smith & Nephew, the content cannot be replicated, printed totally/partially or disclosed in any other way, and anyone must use it as per the requirements, either expressed or implied by Smith & Nephew.

Study Protocol - Device	Smith+Nephew
A Prospective, Multi-center, Randomized Clinical Study to Evaluate the Safety and Effectiveness of Biosure Regenesorb Interference Screw in Arthroscopic Reconstruction of Cruciate Ligaments in Chinese Patients	Study No.: BIOSURE RG.SMD.PMA.2019.01
	Version: V2.0/July 3rd, 2020
	Page 40 of 74

Mainly observe bone ingrowth into screw of the absorbable screw after implantation.

X-ray films, CT images and MRI images are taken during the postoperative 24-month follow-up to mainly observe absorption of the absorbable screw after implantation. All imaging observations are reported in CRF.

The specific imaging evaluation requirements will be provided in a separate document to radiologists for evaluation of examination results.

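### The declared evaluator blinding is not extended to imaging: two sections name different readers, neither states masking, and the descriptive between-arm imaging results are exposed to detection bias

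*Combined protocol and SAP*

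**What the plan says.** On blinding in general, section 10.1.2 states: "This study is designed as a prospective, multi-center, randomized, evaluator-blinded, parallel-controlled study". Section 10.1.3.2 puts this into effect through one independent rater per site, "who is blinded and responsible for completing scoring at each follow-up". Section 10.1.3.5 describes the endpoints covered by scorer training by example: "such as Lysholm score, IKDC score, drawer test and lachman score) in each site".

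On imaging, section 10.1.3.6, which sits among the measures against bias, says that "imaging evaluation will be performed pre-op, 6, 12 and 24 months post-op". It names no reader and does not mention masking. Section 10.1.5.2 says that "imaging evaluation will be performed at each site by the investigator". It keeps all images at the site in DICOM format "in case further evaluation by an independent centralized reviewer is requested by NMPA", and requires them to be altered to protect the subject's identity if they are sent out. Section 10.2.2.9 says: "The specific imaging evaluation requirements will be provided in a separate document to radiologists for evaluation of examination results".

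On what imaging is for, it is a secondary efficacy endpoint at 6, 12 and 24 months. Section 10.1.2 adds that "24-month follow-up will be made to observe the long-term performance and absorbability of the investigational device".

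**The concern.** In an open-implant trial, evaluator blinding is what stands between knowledge of the arm and the recorded outcome. Here the text gives that protection to the rater who does the scoring and does not carry it over to whoever reads the images.

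Imaging needs it. Bone ingrowth and screw absorption are judged by eye from X-ray, CT and MRI, and the protocol gives no grading scale. Section 8.1 also states a directional expectation from preclinical work: the new screw gave way to bone inside 24 months, while the control might still be incompletely absorbed at 3 to 5 years. A reader who knows both the arm and that expectation may lean towards it without meaning to.

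At stake are the between-arm imaging summaries. Those at 6 and 12 months fall within the data to be submitted for registration, and those at 24 months serve the absorbability observation.

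**Working it through.** No figure in the plan bears on this point. The sample size calculation is for the 12-month Lysholm score and does not depend on who reads the images. The check is therefore a comparison of passages.

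1. **Who reads the images?** Section 10.1.5.2 says the investigator at each site. Section 10.2.2.9 says radiologists, working to a separate document. Both sections send the observations to the case report form, so one data field has two candidate readers. A radiologist could be an authorised investigator, or could report to one, but no section says so.

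2. **Is the reader the blinded rater?** Section 10.1.3.2 makes that rater responsible for scoring. The four assessments named in 10.1.3.5 are Lysholm, IKDC, drawer and Lachman. The list is given by example, so imaging is not excluded outright. Imaging has its own paragraph in 10.1.3.6, however, which gives timing only, and 10.1.5.2 then assigns it to the investigator rather than to the blinded rater.

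3. **Could the reader know the arm?** Section 10.2.2.3 has the labels of the implanted components attached to the operative medical record. The arm can be seen in the site file, and nothing bars the image reader from it.

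4. **Is there a prior expectation?** Yes. It is in section 8.1 of the protocol itself, on which section 10.1.3.8 requires investigators to be trained.

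5. **Does the fallback close the gap?** Only in part. Independent review depends on a regulator's request. The image modification is there to protect identity, applies only to images that leave the site, and says nothing about arm. Masking of the independent reviewer is not stated either.

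6. **What depends on the readings?** Section 12.1.4 gives secondary endpoints summary statistics only. Section 12.5 rests success on the 12-month Lysholm score alone. The exposure stops at the descriptive imaging comparison.

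**The case against.** The strongest reply is that the point rests on silence. The imaging instructions are in a separate document that was not available, and masking could well be set out there. The whole study is declared evaluator-blinded, and the list of scored endpoints is open-ended. This stands as a limit: what can be said is that the protocol does not state masking, not that the readings will be made unmasked. It does not answer the point, because a document for radiologists would leave the assignment to the investigator in 10.1.5.2 in place.

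A second reply is that imaging is secondary and descriptive, and that every image is stored, so a doubtful reading can be checked later. Both are true and both limit the weight of the point. But a descriptive summary by arm can still be biased, and the re-reading is not planned.

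A third reply is that masking may fail anyway, because the new screw differs in material and has an open structure. That is a fair limit on the benefit. Keeping the reader away from the operative record still removes one certain source of knowledge.

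A reader might infer more than the text supports. That the implanting surgeon reads the images is possible under 10.1.5.2, but no section says it.

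**Conclusion.** The point holds as an inconsistency between two sections and a gap in the stated blinding. Followed as written, section 10.1.5.2 allows someone who knows the arm to judge ingrowth and absorption. This weakens the between-arm imaging results at 6, 12 and 24 months. Any bias would probably follow the stated expectation and so favour the investigational screw.

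Its size cannot be derived. The documents give no imaging scale, no responder definition, no expected rate and no reader error rate, so any number would be invented.

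Two stronger conclusions might be drawn, and neither is supported. One is that imaging cannot support any statement about the device: section 10.1.2 frames the 24-month follow-up as observation of the investigational device, no imaging hypothesis is tested, and the stored images can be read again. The other is that the trial's main result is at risk: it rests on the Lysholm score, for which a blinded rater is specified.

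The verdict assumes that the separate imaging document does not already name one masked reader. If it does, what remains is to correct 10.1.5.2 to match. The point is a minor improvement, worth making because it is cheap.

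**What to change.** - **Reconcile 10.1.5.2 and 10.2.2.9.** The radiologists already named in 10.2.2.9 make the case report form reading at each site, and the investigator does not score imaging.
- **Mask the reading.** It is made from de-identified DICOM files, without access to the allocation or the operative record.
- **State the scope of blinding.** Say in 10.1.3.2 and 10.1.3.6 that evaluator blinding covers imaging, and repeat this in the separate imaging document.
- **Record how well masking worked.** After each reading, the reader notes whether the device could be identified. Summarise the answers by arm beside the imaging results.

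No extra reader, visit, scan or subject is needed. The cost is protocol wording and file handling. With three modalities at three follow-up visits there are 3 × 3 = 9 image sets per subject, or at most 9 × 140 = 1,260 with no dropout, not counting the early postoperative and optional 3-month images. The files are already kept as DICOM, but the present de-identification step covers only images sent out, so each site needs a simple masked workflow. Masking may remain incomplete because the screws differ in structure and material; the recorded answers would show how far.

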10.1.6 Safety evaluation method

10.1.6.1 Description of safety parameters

No formal hypothesis testing is performed for safety analysis. Descriptive statistics will be used to summarize safety events.

10.1.6.2 Safety evaluation contents

Safety evaluation includes the following contents:

- Incidence (%) and frequency (number of events) of AEs related to device;
- Incidence (%) and frequency (number of events) of adverse events;

Confidential and Proprietary

This document contains confidential and proprietary information on Smith & Nephew PLC and Smith & Nephew, Inc. and is only available to Smith & Nephew and its manufacturers. Without prior written approval of Smith & Nephew, the content cannot be replicated, printed totally/partially or disclosed in any other way, and anyone must use it as per the requirements, either expressed or implied by Smith & Nephew.

Study Protocol - Device	Smith+Nephew
A Prospective, Multi-center, Randomized Clinical Study to Evaluate the Safety and Effectiveness of Biosure Regenesorb Interference Screw in Arthroscopic Reconstruction of Cruciate Ligaments in Chinese Patients	Study No.: BIOSURE
	RG.SMD.PMA.2019.01
	Version: V2.0/July 3rd, 2020
	Page 33 of 74

- Incidence (%) and frequency (number of events) of device deficiencies;
- Reoperation rate.

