6.2 Study contents

This clinical trial is designed to be a prospective, multi-center, randomized, evaluator-blinded, parallel-controlled, non-inferiority trial. The primary efficacy endpoints are not inferior to the control group. The Biosure Regenesorb Interference Screw and BIOSURE HA Interference Screw are used in the trial and control groups, respectively, to evaluate the safety and effectiveness of the investigational medical device Biosure Regenesorb Interference Screw in clinical repair or reconstruction of knee cruciate ligament rupture or tear.

The subjects complying with the criteria for inclusion in this clinical trial will receive 24-month follow-up after being treated with the investigational product or the control product. The following endpoints will be recorded and evaluated: Lysholm score, IKDC score, Drawer test, Lachman test and imaging evaluation results at the follow-up visit at month 6, 12 and 24 after the operation, respectively, incidence and frequency of ADEs, AEs, and device deficiency throughout the trial and reoperation rate.

7 Background of Clinical Trial

The knee becomes one of the most injured joints due to its anatomical structure and particular function in human body. According to the statistics, there are 200,000 ACL rupture cases per year in the United States, including 100,000 requiring ACL reconstruction. An epidemiological investigation in sport injury showed that the total incidence of ACL injury is 0.47% in China. PCL injury are relatively infrequent. As reported in foreign literature, PCL injury has an incidence of 3% in the common population and account for 20% of knee ligament injury. No similar reports are found in China.

The ACL femoral attachment, located at the posterior part of the medial side of the lateral femoral

Confidential and Proprietary

This document contains confidential and proprietary information on Smith & Nephew PLC and Smith & Nephew, Inc. and is only available to Smith & Nephew and its manufacturers. Without prior written approval of Smith & Nephew, the content cannot be replicated, printed totally/partially or disclosed in any other way, and anyone must use it as per the requirements, either expressed or implied by Smith & Nephew.

Study Protocol - Device	Smith+Nephew

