12.4 Expected drop-out rate

Expected drop-out rate is not more than 20%.

Confidential and Proprietary

This document contains confidential and proprietary information on Smith & Nephew PLC and Smith & Nephew, Inc. and is only available to Smith & Nephew and its manufacturers. Without prior written approval of Smith & Nephew, the content cannot be replicated, printed totally/partially or disclosed in any other way, and anyone must use it as per the requirements, either expressed or implied by Smith & Nephew.

Study Protocol - Device	Smith+Nephew
A Prospective, Multi-center, Randomized Clinical Study to Evaluate the Safety and Effectiveness of Biosure Regenesorb Interference Screw in Arthroscopic Reconstruction of Cruciate Ligaments in Chinese Patients	Study No.: BIOSURE RG.SMD.PMA.2019.01
	Version: V2.0/July 3rd, 2020
	Page 48 of 74

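### The reoperation rate has no time point, and crude safety percentages count early losses as event-free, which modestly understates the 24-month risk

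*Combined protocol and SAP*

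**What the plan says.** The safety measures in section 10.1.6.2 are "Incidence (%) and frequency (number of events) of AEs related to device", the same pair for all AEs and for device deficiencies, and "Reoperation rate". Section 10.1.6.1 states: "No formal hypothesis testing is performed for safety analysis. Descriptive statistics will be used to summarize safety events". Section 12.1.1 assigns safety indicators to the safety set and summarises categorical variables by frequency and percentage. Section 12.9.3 sets no minimum follow-up for that set. (Its wording names only the investigational device; I read it as covering both arms.)

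On time, section 6.2 records "incidence and frequency of ADEs, AEs, and device deficiency throughout the trial and reoperation rate". AEs and deficiencies therefore have a loose horizon, and the synopsis gives every subject the same 24-month follow-up. No horizon is attached to reoperation, although the visit schedule collects it at every contact from week 6.

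On incomplete follow-up, section 12.4 expects drop-out of no more than 20%, and section 10.1.4.4 does not require follow-up after withdrawal. Last observation carried forward (sections 12.7 and 12.9.1) applies only to the primary endpoint. No section says how a subject lost early enters a safety figure.

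On reporting, sections 10.1.2 and 10.1.4.7 send 12-month data to the regulator and continue observation to month 24. No cut-off is stated for the safety data in the registration report.

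**The concern.** A percentage of the whole safety set is an unbiased estimate of the risk to a stated time only if everyone is observed to that time. A subject who leaves at month 4 without a reoperation adds one to the denominator and nothing to the numerator, whatever happens later. The percentage is then too low. If one arm loses more subjects, that arm looks safer even when the true risks are equal.

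Comparing safety is part of the stated trial objective (section 6.1), and reoperation is one of four listed safety indicators. A rate without a time point cannot be set against a 12-month or a 24-month figure from elsewhere, and two analysts could compute it differently from the same data.

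**Working it through.** **The plan's own figures.** The plan gives no AE or reoperation rate to reproduce. Its sample size fixes the number per arm: with margin 5, spread 9 used as the standard deviation, one-sided 0.025 and 80% power, n = 2 × (1.960 + 0.842)² × 81 / 25 = 50.9, so 51. Then 51 / 0.8 = 63.75, so 64; and 2 × 64 + 12 = 140, or 70 per arm. These match section 12.2.1.

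**Assumptions not in the documents.** Constant hazard; true 24-month risk 8% (5% and 10% also examined); drop-out unrelated to events. Section 12.4 does not say by when the 20% is reached, so two patterns are used: evenly over 24 months, and evenly over the first 12.

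**Step 1, hazard.** λ = −ln(1 − 0.08) / 24 = 0.003474 per month. The 12-month risk is 1 − exp(−12λ) = 4.08%.

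**Step 2, events seen in those who leave.** If the leaving time is uniform on 0 to T, the mean probability of an event before leaving is 1 − (1 − exp(−λT)) / (λT).
- T = 24: 1 − 0.0800 / 0.08338 = 4.06%.
- T = 12: 1 − 0.04083 / 0.04169 = 2.06%.

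**Step 3, crude 24-month percentage** = (1 − d) × 8% + d × (Step 2).

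| Drop-out d | Spread over 24 months | Spread over first 12 months |
|---|---|---|
| 10% | 7.61% | 7.41% |
| 20% | 7.21% | 6.81% |
| 30% | 6.82% | 6.22% |

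At 20% the shortfall is 0.79 or 1.19 points, which is 10% or 15% of 8%. If every drop-out left on day 0 the figure would be 0.8 × 8% = 6.4%, a 20% shortfall; this is the limit when drop-out is unrelated to events. With a constant drop-out hazard, the crude figure is 4.5% for a true 5% and 9.0% for a true 10%. If half the events fall in the first 3 months, these become 4.7% and 9.3%.

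**Step 4, between arms.** Equal drop-out lowers both arms alike in relative terms. With equal true risk but 10% against 30% drop-out, the crude figures are 7.6% against 6.8%, or 7.4% against 6.2%: a false gap of 0.8 or 1.2 points. The standard error of a difference at 8% with 70 per arm is √(2 × 0.08 × 0.92 / 70) = 4.6 points. For one arm, 4 events in 70 is 5.7%, with an exact 95% CI of 1.6% to 14.0%.

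**Step 5, registration report.** "The enrollment of subjects is planned to last for about 12 months" If, and only if, that report pooled all events known when the last subject reached month 12, follow-up would run from 12 to 24 months. Without drop-out, the crude figure would be 1 − (exp(−12λ) − exp(−24λ)) / (12λ) = 6.06%, against a 12-month risk of 4.08%: a ratio of 1.48, and upward.

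**The case against.** Several objections stand and limit the point.

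- AEs do have a horizon: they are recorded throughout the trial, over the same planned 24 months for everyone. The missing time point is specific to reoperation.
- A reader might infer that staggered entry also makes the rates too low. The documents do not support that. At the 24-month analysis all subjects have the same planned follow-up. Entry time matters only if the registration report includes events after month 12, and it would then raise the figure above the 12-month risk. Sections 10.1.2 and 10.1.4.7 speak of 12-month data and do not say that later events are pooled, so Step 5 is a possibility left open and not a description of the plan.
- The bias is small. A shortfall of 0.8 to 1.2 points is less than one subject in 70, 20% is a ceiling, and the 10% against 30% split is invented for illustration.
- Safety is descriptive, and the acceptance criterion in section 12.5 uses only the Lysholm score.
- The plan works against loss: telephone contacts (section 10.2.2.6), documented contact attempts (section 10.1.4.5), and an effort to complete the final evaluation (section 10.1.4.4).
- Kaplan-Meier is not a full cure. It assumes that censoring is unrelated to events, yet an SAE is a listed withdrawal reason in section 10.1.4.4. No contact is scheduled between months 12 and 24, and the visit windows are wide (days 305-426 and 670-790).

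One objection does not carry: that the denominator is unknown. Sections 12.1.1 and 12.9.3 together point to a percentage of the safety set, and nothing in them removes subjects lost early. The limits of Kaplan-Meier reduce the gain but do not make the crude percentage better.

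**Conclusion.** The point holds in a limited form. The reoperation rate lacks a time point, and safety percentages taken over the safety set count early losses as event-free. Under the stated assumptions (constant hazard, 8% true risk, 20% drop-out unrelated to events), the crude 24-month figure is about 7.2% or 6.8%. This understatement is modest and well inside the sampling error of this trial.

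Two stronger conclusions are not supported. One is that the comparison between arms is biased as planned: that needs drop-out that differs by arm or relates to events. The second is possible, because an SAE is a withdrawal reason and section 13.2 links loss to follow-up in previous studies to limited recovery; the bias could then exceed the limits shown. The other is that staggered entry depresses the rates, which it does not.

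The change is worth making because it is cheap and gives the reoperation figure a defined meaning. The primary conclusion does not depend on it.

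**What to change.** In section 10.1.6.2 and section 12:

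1. Define time from implantation to first reoperation, and to first device-related AE.
2. Report Kaplan-Meier cumulative incidence by arm, with 95% CI and numbers at risk, at a fixed day for month 12 (registration report) and a fixed day for month 24 (final report), censoring at last contact. Choose the days with the visit windows in mind, so that few subjects are censored just short of them.
3. Keep the planned counts and percentages. In the registration report, limit safety counts to events up to the same fixed month-12 day.
4. Confirm that the CRF records the date of each reoperation. AE onset date is already part of the investigator's report (section 16.3.1).
5. Tabulate reasons for withdrawal by arm, so that a reader can judge whether censoring is related to events.

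**Cost:** a few lines of text and one standard procedure, with no extra visits or subjects. The reported rates may be slightly less favourable. Censoring times in the second year will be coarse, and the estimate relies on non-informative censoring.
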